Turmeric Based Therapy in the Treatment of Psoriasis: A Clinical Trial

Date 24 August 2019

Study Protocol

[name]

Introduction

Psoriasis is a prevalent skin disorder. It affects around 4% of world's population. It can be disfiguring and disabling in severe cases. Psoriasis has been associated with many comorbidities e.g. increased cardiovascular risk, diabetes and metabolic syndrome (Cai et al., 2013; Mahil et al., 2016).

The exact cause of psoriasis is still unknown, however, in a genetically susceptible individual there is evident dysregulated immune response to an unknown stimulus (Mitra et al., 2013; Mahil et al., 2016). There is dysregulation of the mechanisms present in the skin to upregulate or to down regulate the immune responses when needed (Wang et al., 2011). Such dysregulation results in abnormal continuous inflammatory loop observed in psoriasis. In psoriasis there are specific pathways continuously activated including Th1 pathway with TNFa, IL6 and IL 12 upregulation and Th17 pathway with increased expression of IL17 and IL23. When exposed to environmental triggers, self-RNA and self-DNA released from stressed keratinocytes got complexed with / Cathelicidine (LL37). The formed complexes interact with Toll like receptors (TLRs) of plasmacytoid dendritic cells (pDCs). On their activation, pDCs produce interferon-α (IFN-α). INFα orchestrates the maturation of monocyte derived dendritic cells (moDCs). Moreover, self-RNA / LL37 complexes and viral ssRNA directly enhance the maturation of IFN- α -primed moDCs both on phenotypical and functional levels. The moDCs maturation is further promoted by TNF- α , IL-1 β , INF- γ , IL-6, secreted from stressed keratinocytes, fibroblasts, lymphocytes, natural killer T cells and macrophages. Mature IFN-α-primed moDCs migrate to draining lymph nodes, where they drive naive T cell differentiation into Th1

and/or Th17 cells through IL-12 and IL-23. These T cells migrate via lymphatic and blood vessels into psoriatic dermis and contribute to the formation of a psoriatic plaque (Farkas & Kemény, 2012).

Nuclear factor κB (NF-κB) is a transcription factor that orchestrates inflammation and other complex biological processes including cellular proliferation, differentiation and apoptosis. It also controls various cytokines and chemokines production. It has a major role in psoriasis development; its activation and nuclear translocation is present in every step of the way of psoriasis starting from stressed keratinocyte release of cytokines to maturation and activation of dendritic cells to the continuous loop of T cell activation. Inducers of NF-kB include pro-inflammatory cytokines, such as TNF-α and IL-1, foreign antigens, such as carbohydrates and peptides recognized by pattern recognition molecules as TLRs (Goldminz et al., 2013). Induction of NF-κB leads to its nuclear translocation with alteration of cell cycle and apoptosis in keratinocyte along with immune cell activation and cytokine release (Tsuruta, 2009). NF-κB is a central point in psoriasis pathogenesis and its level is elevated in psoriatic skin (Lizzul et al., 2005) and is reduced with successful treatment with anti TNF- α therapies (Lizzul et al., 2005; Avramidis et al., 2010). Glucocorticoids competitively inhibit NF-κB binding. NF-κB represents a potential target for antipsoriatic therapy (Goldminz et al., 2013).

Curcuma longa (Linn) (turmeric) is a rhizomatous herbaceous plant. Its extract Curcumin (diferuloylmethane) has gained an increasing interest for its pro apoptotic properties inhibiting cell proliferation. So it has been tested for its anticancer efficacy in animal models of pancreatic cancer, breast cancer, colorectal cancer and skin cancer (Kang et al., 2016). Turmeric

extract has also showed phosphorylase kinase inhibition activity, hence an anti-inflammatory, anti-oxidant, anti-microbial and anti-carcinogenic effects. It has inhibitory effects on NF-κB and various cytokines production (Sun et al., 2013). Curcumin, the turmeric extract, inactivated NF-κB and subsequently reduced the expression of multiple proinflammatory cytokines including TNF-α, IL-1, IL-2, IL-6, IL-8, and IL-12 (Sugimoto et al., 2002; Camacho-Barquero et al., 2007; Sun et al., 2013). Curcumin also suppresses the activation of other transcriptional factors including signal transducer and activator of transcription (STAT1, STAT3, and STAT4) (Sun et al., 2013). Both STAT3 & STAT4 are major contributors in T helper differentiation toward Th17 and Th1 respectively. STAT3 also regulate keratinocyte proliferation in psoriasis (Coimbra et al., 2012). Curcumin also has been proved to act as a potent blocker of different types of K channels. K channels play a very important role in T cell activation and differentiation. Blockers of K channels have been under investigation for autoimmune disease management in phase I clinical study (Kang et al., **2016)**.

The complex nature of psoriasis pathogenesis has imposed the need of many therapeutics. Each targets specific point in the disease pathogenesis. Despite the presence of various systemic and topical therapies, World Health Organization (WHO) global report on psoriasis has highlighted the psoriasis patients' need to have more treatment options (World Health Organization (WHO), 2016).

Turmeric extract has been used for ages in treatment of different diseases as part of alternative medicine. Its effectiveness has been studied in different

dermatologic diseases e.g. acne, eczema, oral lichen planus and psoriasis (Vaughn et al., 2016).

Many other natural remedies have been tried for treatment of psoriasis and other skin disease (Vaughn et al., 2016). There is a trend in patients to ask for herbal natural remedies as a safe, effective and affordable alternative or adjuvant to conventional therapeutics (Deng et al., 2013; Talbott et al., 2015).

Rationale

- •Psoriasis is a prevalent disabling and disfiguring dermatologic condition. WHO resolution on psoriasis has recognized the inadequate treatment options psoriasis patients suffer among other problems. The available treatment options have many side effects. A lot of the effective treatment options are either expensive or not appropriate for hepatic patients who represent a large subset of Egyptian psoriatic patients. This highlights the need for inexpensive and safe alternative.
- Few reports are published on the effectiveness of Turmeric in psoriasis treatment. Having an immune modulatory effect especially as anti NFkB it is expected to be effective therapy with minimal side effect.
- •Up to our knowledge this is the first study addressing the efficacy of combined turmeric and olive oil based topical therapy in psoriasis treatment.

Research question

What is the efficacy of Turmeric based topical therapy in the treatment of psoriasis?

Hypothesis

 Turmeric based therapy effectively treat psoriasis through reduction of NFκB expression in psoriatic skin.

Aim

The aim of this study is to verify the efficacy of Turmeric based therapy alone and combined with olive oil in the treatment of psoriasis.

Objectives

- 1- To evaluate the effectiveness of Turmeric extract based topical therapy for psoriasis
- 2- To compare the effectiveness of Turmeric extract based therapy and combined Turmeric/Olive oil based therapy.
- 3- To identify the effect of Turmeric based therapy of NFκB expression in psoriasis.

Subjects and methods

Technical design

• **Setting:** Dermatology, Venereology & Andrology Department, Faculty of Medicine Zagazig University, Pathology Department, Faculty of Medicine Zagazig University.

Study design:

• Type of study:

Clinical trial

• Sample size:

The sample size is calculated using OpenEpi with PASI score of the control group is 3.3 ± 2 and of the Turmeric treated group is 1.4 ± 1.1 . So at power of study 80 % and CI 95% the sample size is calculated to be 40 with 10 subjects in each group.

• Inclusion criteria

All participants must be willing to sign informed consent.

The study will include

For the patients group:

- 1- Patients with mild to moderate psoriasis vulgaris of any age & gender.
- 2- Patient didn't receive any systemic or topical therapy for psoriasis the last 4 weeks.

For the control group:

- 1- Psoriasis vulgaris patients (mild to moderate) of matching age and gender.
- 2- Patients didn't receive any systemic or topical therapy for psoriasis the last 4 weeks

Exclusion criteria

- 1. Patients previously received topical or systemic therapy for psoriasis in the past 4 weeks.
- 2. Patients with pustular or erythrodermic psoriasis.
- 3. Patients with other dermatological diseases.

4. Patients have hypersensitivity from the active ingredients of the therapy.

Study groups

Four groups will be included in the study

Group 1: 10 psoriatic patients will receive Turmeric extract based topical therapy for at least 4 weeks up to 12 weeks.

Group 2: 10 psoriatic patients will receive Turmeric and Olive oil based topical therapy for at least 4 weeks up to 12 weeks.

Group 3: 10 psoriatic patients will receive only the base topical therapy for at least 4 weeks up to 12 weeks.

Group 4: 10 psoriatic patients will receive 2 sessions of NB-UVB every week for at least 4 weeks up to 12 weeks.

Group 5: 10 psoriatic patients will receive daily Betamethasone or Calcipotriol every week for at least 4 weeks up to 12 weeks.

Steps of study:

- All study subjects will be subjected to:
- I. History Taking: Detailed history will be taken from patients regarding name, age, duration of disease, arthropathy, family history of the disease, other dermatologic conditions, other systemic diseases and drug history
- II. Clinical evaluation: Assessment of the psoriasis using PASI score.
- III. *Dermoscopic evaluation*: The psoriatic plaques will be assessed using dermoscope. The dermsoccopic criteria of psoriasis includes dotted vessels regulary distributed on light red background with white silvery scales homogenously distributed on the erythematous background.

- IV. *Histopathologic assessment*: 5 ml punch Skin biopsies will be obtained and immersed in 10% formalin then embedded in paraffin wax and processed for H&E staining. The diagnosis of psoriasis will be histologically confirmed.
- V. *Immunohistochemical analysis*: NFκB expression in the psoriatic skin will be evaluated before and after treatment using immunohistochemical stain.

Administrative design

All patients included in the study will provide written informed consent after being informed about the study steps, the possible complications and their capability to withdraw at any time after approval of Institutional Review Board Of Faculty of Medicine, Zagazig University.

Results

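### The trial is sized on PASI but no primary outcome is designated, and the role of NFκB in a claim of efficacy is left open

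*Protocol*

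**What the plan says.** All references are to the protocol.

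- **Research question:** "What is the efficacy of Turmeric based topical therapy in the treatment of psoriasis". No measure is named.
- **Hypothesis (the only one):** "Turmeric based therapy effectively treat psoriasis through reduction of NFκB expression in psoriatic skin". It joins a clinical effect to a mechanism, and NFκB is the only measurable quantity in it.
- **Objectives:** the first is "To evaluate the effectiveness of Turmeric extract based topical therapy for psoriasis", and the second compares the two turmeric preparations on effectiveness. Neither names a measure. The third is "To identify the effect of Turmeric based therapy of NFκB expression in psoriasis". They are numbered, but none is called primary.
- **Sample size:** "The sample size is calculated using OpenEpi with PASI score of the control group", put at 3.3 ± 2, against 1.4 ± 1.1 with turmeric, at 80% power and a 95% confidence level, giving 10 per group and 40 in all. No effect size or SD is given for NFκB.
- **Steps of study:** PASI, dermoscopy, histopathology and NFκB immunohistochemistry. Only NFκB is expressly measured both before and after treatment. Histopathology is there to confirm the diagnosis. Dermoscopy has neither a score nor a follow-up time.
- **Study groups:** treatment lasts from 4 to 12 weeks, with no fixed assessment time.
- **Results:** appropriate methods will be used, with no further detail.

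**The concern.** A power statement has meaning only for the outcome that decides the trial, and this protocol does not say which outcome that is. The Sample size paragraph leads a reader to PASI. The hypothesis, the third objective and the before-and-after wording for NFκB allow another reader to give NFκB equal or greater weight.

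At stake is how a split result would be read. If PASI showed no difference and NFκB did, or the reverse, nothing in the text prevents either result from being presented as evidence that turmeric works. The 5% error rate implied by the 95% confidence level would not apply to a conclusion reached that way. Once the data are seen, the choice can no longer be made without bias.

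**Working it through.** **1. What the sizing covers.** Inputs from Sample size: means 3.3 and 1.4 (difference 1.9), SDs 2 and 1.1, power 80%, and a 95% confidence level, read here as two-sided α = 0.05 because sidedness is not stated.

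n per group = (SD₁² + SD₂²)(z₀.₉₇₅ + z₀.₈₀)² / difference²
= (4 + 1.21)(1.960 + 0.842)² / 1.9²
= 5.21 × 7.849 / 3.61 = 11.33, so 12 per group. The protocol states 10.

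Power at 10 per group:
- Standard error = √(5.21/10) = 0.722, and 1.9/0.722 = 2.632.
- Normal approximation: Φ(2.632 − 1.960) = 74.9%.
- Two-sample t-test, 18 degrees of freedom, average variance 5.21/2: 70.2%.

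A one-sided calculation gives 9 per group. None of the variants tried gives exactly 10. The stated 80% therefore concerns PASI only, and the inputs do not reproduce it.

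**2. What the sizing says about NFκB.** Nothing, since no NFκB difference or SD is given. In standardised terms, 10 patients per group give 80% power at:
- about 1.32 SD for a comparison of two groups (noncentral t, 18 df);
- about 1.0 SD of the change for a before-after comparison within one group (noncentral t, 9 df).

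The protocol does not say which comparison applies. Neither figure shows that NFκB is under-sized.

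**3. Error rate if either outcome may decide.** Assume one turmeric-versus-control comparison, 10 per group, no true effect, PASI and NFκB each tested at two-sided 5%, and a claim made if at least one is positive.

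- Independent outcomes: 1 − 0.95² = 9.75%.
- Correlation 0.5 (assumed, simulated): about 9.1%.
- Correlation 0.8 (assumed, simulated): about 7.9%.

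**4. Error rate if both must be positive.** Independent outcomes: 0.05² = 0.25%. In simulation the rate is about 1% at correlation 0.5 and about 2% at 0.8.

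So the rate for the main claim lies below or above 5% depending on a rule that the protocol does not give.

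**The case against.** The strongest reply is that the text already points to an order. The research question, the aim and the first two objectives concern efficacy; PASI is the only clinical score and the only sizing variable; NFκB comes third. On that reading only a label is missing. A second reply is that no passage says either outcome suffices. If the joint hypothesis requires both, the error rate is below 5%. A third is that multiplicity rules are commonly left to a SAP, which is not shown.

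Much of this stands. PASI is the natural primary outcome, and the 8% to 10% is conditional on an either-one-suffices rule. But an implied order is not a designation, and naming the primary outcome is the protocol's task even where the test rules are left to a SAP.

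Three stronger readings are tempting, and the document does not support them:

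- **A reader might infer that the hypothesis concerns NFκB alone and so conflicts with sizing on PASI.** It also asserts that the therapy treats psoriasis effectively, which PASI can measure.
- **A reader might count four competing outcomes, which would give a false-positive chance of about 11% to 18%.** Histopathology is for diagnosis, and dermoscopy has no scoring or follow-up. Only PASI and NFκB are supported as efficacy outcomes.
- **A reader might take 1.32 SD as the detectable NFκB effect.** That holds for a two-group comparison only; a paired before-after test gives about 1.0 SD.

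**Conclusion.** The point holds in a limited form. The protocol sizes the trial on PASI without designating it primary, and leaves the role of NFκB unstated. If either outcome could support an efficacy claim, the false-positive chance for one turmeric-versus-control comparison would be about 8% to 10% instead of 5%. This rests on two-sided 5% tests, assumed correlations from 0.8 to 0, and a decision rule that the protocol neither states nor excludes. Additional group comparisons and a free choice of assessment time between 4 and 12 weeks could raise it; they are not in the figure.

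This should be corrected: it bears on the trial's main conclusion and costs little to settle. It does not show that the hypothesis and the sample size contradict each other.

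**What to change.** In Objectives and Sample size, state that:

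1. PASI is the primary outcome, in one named turmeric-versus-control comparison and at one fixed assessment time within the 4 to 12 week period. Name the turmeric group, and say which listed group is the control of the calculation; base-only, NB-UVB and betamethasone or calcipotriol groups are all listed.
2. The power statement covers that comparison only.
3. NFκB is a secondary, mechanistic outcome that cannot by itself support a claim of efficacy.
4. Dermoscopy is descriptive and histopathology diagnostic.

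Restate the power from the protocol's own inputs, about 70% by t-test or 75% by normal approximation at 10 per group, instead of repeating 80%.

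The cost is a few sentences, with no new data or patients. The downsides are that a positive NFκB result with a negative PASI result can no longer be reported as success, and that the stated power looks less favourable.

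### The protocol's own PASI inputs need 12 or 13 patients per group for 80% power, not 10; baseline PASI plays no part in the sizing, and adjusting for it would close the gap only at an assumed correlation of about 0.53 or more

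*Protocol*

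**What the plan says.** The Protocol's Sample size paragraph (under Study design) rests on two group summaries: "The sample size is calculated using OpenEpi with PASI score of the control group is 3.3" (± 2) and, for the other arm, "of the Turmeric treated group is 1.4 ± 1.1". The criteria are "at power of study 80 % and CI 95"%, and the conclusion is that "the sample size is calculated to be 40 with 10 subjects in each group". No baseline value, change from baseline or correlation enters the calculation.

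Under Inclusion criteria, the controls are "Psoriasis vulgaris patients (mild to moderate) of matching age and gender". The treated patients are also restricted to mild to moderate disease.

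Under Steps of study, item II applies to all subjects: "Clinical evaluation: Assessment of the psoriasis using PASI score". It names no time point. Item V says that NFκB is measured before and after treatment. The Results section leaves the choice of statistical methods open.

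The Study groups section opens with "Four groups will be included in the study" and then lists five groups of 10.

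**The concern.** The sample size is the only place where the protocol quantifies a comparison, and the effect it assumes is large: 1.9 PASI points, or 1.18 standard deviations. The stated power should therefore be easy to reproduce from the printed inputs, and it is not. If the true power is 70 to 75%, the chance of missing the planned effect is 25 to 30% rather than 20%.

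The second question is whether something the trial probably measures anyway could make up the shortfall. With 10 per arm, groups can start at different PASI levels by chance, and a comparison of raw final scores carries that difference into the result. Adjusting for baseline PASI removes it and needs no extra patients. How much power this returns depends on how strongly baseline and final PASI are correlated.

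**Working it through.** **Inputs (Protocol, Sample size).** Means 3.3 and 1.4, so the difference is 1.9. SDs 2 and 1.1, reading ± as SD. Power 80%. The 95% confidence level is read as two-sided α = 0.05. Stated result: 10 per group.

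**Step 1: reproduce the stated size.** For two independent means with unequal SDs,

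n per group = (SD₁² + SD₂²)(z₀.₉₇₅ + z₀.₈₀)² / difference²
= (4 + 1.21)(1.960 + 0.842)² / 1.9² = 11.33, so 12 per group.

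This does not reproduce 10. Other readings do not either:

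| Reading | n per group |
|---|---|
| One-sided α = 0.05 | 9 |
| SD 2 in both arms | 18 |
| SD 1.1 in both arms | 6 |
| Bonferroni, 2 comparisons | 14 |
| Bonferroni, 3 comparisons | 16 |

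**Step 2: power with 10 per group, unadjusted.** Root-mean-square SD = √(5.21/2) = 1.614. Standard error of the difference = √(5.21/10) = 0.722. Ratio = 1.9/0.722 = 2.632.

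- Normal approximation: Φ(2.632 − 1.960) = 74.9%.
- Pooled t-test, 18 df, noncentral t: 70.2%.
- Welch t-test: 68.7%.

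By the pooled t-test, 12 per group gives 78.7% and 13 gives 82.1%, so 13 are needed on that basis.

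**Step 3: size of a chance baseline difference.** The baseline SD is not given. Taking the two printed SDs as a range and assuming chance allocation, the standard error of the baseline difference is SD × √(2/10).

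- SD 2: standard error 0.894; probability of a gap above 1 point 26%.
- SD 1.1: standard error 0.492; probability 4%.

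**Step 4: what baseline adjustment returns at 10 per group.** The correlation ρ between baseline and final PASI is an assumption throughout. The textbook shortcut multiplies the SD by √(1 − ρ²) and uses 17 df. It leaves out the cost of estimating the slope when the arms differ at baseline, and it ignores the unequal SDs. Simulating a two-group ANCOVA with SDs 2 and 1.1 allows for both:

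| Assumed ρ | Shortcut, 17 df | Simulated ANCOVA |
|---|---|---|
| 0 | 69.9% | 67–68% |
| 0.3 | 73.9% | 71–72% |
| 0.4 | 77.2% | 74–75% |
| 0.5 | 81.7% | 78–79% |
| 0.55 | – | 81% |
| 0.6 | 87.3% | 84% |
| 0.7 | 93.5% | 90% |

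Simulated power reaches 80% at ρ of about 0.53. More lenient methods put the threshold lower: 0.34 (normal approximation), 0.39 to 0.41 (error variance pooled over five or four groups), 0.46 (shortcut, 17 df). At ρ = 0.3 every method stays below 80%.

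**Step 5: two qualifications.** Correcting for 2 or 3 comparisons by Bonferroni raises the normal-approximation threshold from 0.34 to 0.52 or 0.58. A simple change score is no substitute: its variance ratio is 2(1 − ρ), which gives 56% power at ρ = 0.3 and only equals the unadjusted test at ρ = 0.5.

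**The case against.** The strongest objection is that a two-mean sample-size formula does not fix the analysis. Sizing unadjusted and analysing adjusted is common. The protocol leaves the methods open, and a statistical analysis plan that is not shown may already contain a baseline covariate. That stands. A reader might infer that baseline PASI goes unused, but the protocol shows this only for the sizing and the matching.

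Three further points also stand:

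- No PASI time point is written. A pre-treatment score is a reasonable inference, because judging efficacy on PASI needs one, but the text states before-and-after measurement only for NFκB.
- Severity is not left wholly uncontrolled, since both patients and controls must have mild to moderate disease. That restriction may also narrow the baseline range and lower the correlation on which the gain depends.
- A reader might infer that ANCOVA rescues 10 per group. The documents give no correlation, and at 0.5 the simulated power is still just under 80%.

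None of this touches the arithmetic. The size and power are stated in the protocol itself, and an analysis plan kept elsewhere would not make 10 follow from those inputs.

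**Conclusion.** The sample-size statement is wrong on its own inputs. Eighty per cent power needs 12 per group (normal approximation) or 13 (t-test), and 10 per group gives about 75% or 70% respectively. This assumes that ± denotes SD and that the 95% level means two-sided α = 0.05 for a single comparison.

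Pre-specified adjustment for baseline PASI is sound and cheap, and the protocol neither plans nor excludes it. Whether it restores 80% with 10 per group is conditional. For one two-group comparison with the protocol's unequal SDs it takes a correlation of about 0.53 or more, and a higher one if several comparisons are corrected for. The documents support neither a claim that the baseline score is ignored in the analysis nor a claim that adjustment will recover the stated power.

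**What to change.** 1. In the Sample size paragraph, restate the power for 10 per group as about 70 to 75% for the unadjusted comparison, or raise the group size to 12 or 13.
2. Under Steps of study, state that PASI is recorded before and after treatment.
3. State that post-treatment PASI is compared by ANCOVA with group and baseline PASI as terms, and NFκB likewise with its pre-treatment value.
4. If 80% is claimed on the adjusted basis, give the assumed correlation and its support, show power over a range such as 0.3 to 0.7, and say how many comparisons are made and whether α is corrected. If about 0.53 cannot be supported, increase the group size.
5. Reconcile the four groups announced with the five listed, since the total depends on it. At 10 per group the total is 40 or 50, and at 12 it is 48 or 60.

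Items 2 and 3 cost a few sentences and one degree of freedom in each analysis. If the correlation were zero, adjustment would lower power slightly, from 70% to about 67 to 68%. Raising the group size to 12 or 13 adds two or three patients per group.

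### Ten patients per group does not give the stated 80% power: on the protocol's own PASI figures (two-sided 5%, equal groups) 12 or 13 are needed, and 10 gives about 75% or 70%

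*Protocol*

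**What the plan says.** The Sample size paragraph (Protocol, Study design) takes its inputs from one pair of PASI figures: "PASI score of the control group is 3.3 ± 2 and of the Turmeric treated group is 1.4 ± 1.1". It then gives the result: "So at power of study 80 % and CI 95% the sample size is calculated to be 40 with 10 subjects in each group". OpenEpi is named as the software, but its settings are not shown. The paragraph gives no sidedness, allocation ratio or test.

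The Study groups section assigns 10 patients to every group it lists. Groups 1 and 2 are the only ones that receive turmeric. The base-only group is described as "Group 3: 10 psoriatic patients will receive only the base topical therapy for at least 4 weeks up to 12 weeks", and the next group is phototherapy: "Group 4: 10 psoriatic patients will receive 2 sessions of NB-UVB every week for at least 4 weeks up to 12 weeks". Objective 2 is "To compare the effectiveness of Turmeric extract based therapy and combined Turmeric/Olive oil based therapy".

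**The concern.** The protocol prints both its inputs and its answer, so the answer can be checked, and it does not follow under the usual reading of those inputs. This is the trial's only justification of its size. A reader told that power is 80% will take a null result as fairly good evidence against the assumed effect. If power is really 70% to 75%, that inference is weaker than advertised.

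**Working it through.** **Inputs (all from the Sample size paragraph).**
- Control: mean 3.3, SD 2. Turmeric: mean 1.4, SD 1.1. The ± figures are read as SDs.
- Difference: 3.3 − 1.4 = 1.9.
- Sum of variances: 2² + 1.1² = 4 + 1.21 = 5.21.
- Power 80%: z = 0.842.
- 95% confidence, read as two-sided 5%: z = 1.960.
- (1.960 + 0.842)² = 7.849 (from unrounded z values).

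**Attempt to reproduce 10 per group, equal allocation.**

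n = (SD₁² + SD₂²)(z_α + z_β)² / difference² = 5.21 × 7.849 / 3.61 = 11.33, so 12 per group.

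The stated 10 is not reproduced. The same formula gives 10.02 if power is set to 75% instead of 80%.

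**Power by group size, two-sided 5%.**

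| n per group | Normal formula | Pooled t-test | Welch t-test |
|---|---|---|---|
| 10 | 74.9% | 70.2% | 68.8% |
| 11 | 78.8% | 74.7% | 73.5% |
| 12 | 82.2% | 78.7% | 77.6% |
| 13 | 85.1% | 82.1% | 81.2% |

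The first entry is Φ(1.9/√(5.21/10) − 1.960) = Φ(1.9/0.722 − 1.960) = Φ(0.672) = 0.749. The t-test columns use the noncentral t distribution. A simulation of the pooled t-test with 200,000 runs per size gave 70.3% at 10, 78.7% at 12 and 82.0% at 13. So 80% power needs 12 per group by the normal formula and 13 by either t-test.

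**Difference detectable with 80% power at 10 per group.** Normal formula: (1.960 + 0.842) × 0.722 = 2.02. Pooled t-test: 2.14. The assumed difference is 1.9.

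**Other routes to 10 or 40.**
- *One-sided 5%, equal groups.* The normal formula gives 8.92, so 9. The pooled t-test gives 9.68, so 10, with 81.2% power.
- *Unequal allocation, two-sided, k treated per control.* n_control = (4 + 1.21/k) × 7.849/3.61.
  - k = 2: 10.01 controls and 20.02 treated. At 10 against 20, power is 80.0% by the normal formula and 72.8% by Welch.
  - k = 3: 9.57 controls and 28.72 treated, about 40 in total after rounding up to tens. At 10 against 30, power is 81.7% by the normal formula and 74.0% by Welch.
- *Simple average of the SDs* ((2 + 1.1)/2 = 1.55), two-sided, equal groups: 11 per group, still not 10.

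**Totals.** On the stated four groups: 4 × 12 = 48 or 4 × 13 = 52, against 40. The Study groups section actually lists five groups of 10. On that count it would be 5 × 12 = 60 or 5 × 13 = 65, against 50.

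**The case against.** The strongest reply is that the error depends on a reading the protocol does not spell out. A one-sided t-test gives exactly 10 per group. A two-sided 3:1 calculation gives 10 controls and about 30 treated, which matches both the 10 and the 40. The eligibility criteria also speak of a patients group and a control group, which would suit a many-to-one layout. So the software may have returned a correct answer to a question the protocol did not record.

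Part of this stands: it cannot be said that 10 is unobtainable, nor how the calculation was really set up. But the protocol states none of these settings, and one-sided testing is not what a 95% confidence level ordinarily means. The 2:1 route has to pool Groups 1 and 2, the very groups that Objective 2 sets out to compare. The 3:1 route needs a third treated group, yet only two groups receive turmeric, so a non-turmeric group such as phototherapy would have to be given the turmeric mean and SD. Neither route powers one turmeric group of 10 against one control group of 10.

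Two smaller points are fair. The protocol does not say which group is the control in the calculation. The base-only group is the natural reading, but the shortfall is the same for any single control group of 10. The protocol also names no test, so the t-test figures rest on a choice of method. The normal formula, the more lenient of the two, still falls short.

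**Conclusion.** The concern holds. With the protocol's own means and SDs, a two-sided 5% level and equal groups, 80% power needs 12 per group (normal formula) or 13 (t-test). The stated 10 gives 74.9% or 70.2%. The gap is 2 or 3 patients per group, or 5 to 10 points of power, and the miss rate is 25% to 30% instead of 20%.

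This rests on three assumptions: the ± figures are SDs, the 95% confidence level is two-sided, and one turmeric group is compared with one control group of the same size. The arithmetic under that reading is firm; which settings were actually entered is unknown. The shortfall is modest and does not undermine the trial by itself, but the stated power should be corrected.

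**What to change.** Replace the concluding sentence of the Sample size paragraph with wording such as: *With 10 patients per group, a two-sided 5% t-test has about 70% power (75% by the normal formula) to detect 3.3 ± 2 versus 1.4 ± 1.1; 80% power would need 12 (normal formula) or 13 (t-test) per group.* Name the group that serves as control.

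If a one-sided test or unequal allocation was intended, state the sidedness, the ratio and which groups are pooled, with the error rate and power that go with them.

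Keeping 10 per group costs no patients, only a less favourable stated power. Restoring 80% costs 8 more patients (48 − 40) or 12 more (52 − 40) on the four-group count, and 10 (60 − 50) or 15 (65 − 50) on the five groups listed.

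Optionally, if PASI is recorded both before and after treatment (the protocol gives no PASI time points), adjusting for baseline PASI would recover some power at 10 per group. The gain depends on an assumed baseline correlation: about 71% to 74% power at 0.3 and 79% to 82% at 0.5.
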